14.2 N/A

14.3 N/A

## **15.0 Potential Benefits to Subjects or Others**

15.1 Autism Eats may prevent problematic mealtime behaviors and promote development of healthy eating habits among children with ASD. Participants may benefit from increased awareness of health factors related to foods that might improve their ability to manage their health in the future. Thus, it is possible that the proposed study will advance the well-being of the participants. Professional

development sessions for EI providers can benefit the providers by training them about the Autism Eats nutrition intervention and healthy eating behaviors in general.

15.2 This novel and timely study may establish potential feasibility and preliminary efficacy of an EI-integrated nutrition intervention that if proven effective could substantially reduce lifetime risk for diet-related chronic conditions among children with ASD. The findings may benefit the field of health promotion, especially promoting health eating habits among children with ASD, by identifying whether an innovative nutrition intervention through the Part C EI services can improve participants' dietary behaviors, problematic mealtime behaviors, and potentially weight status. The benefits of the study to the children with ASD, and to society at large appear to justify the minimal risks. Findings from this study will provide relevant information to determine appropriate nutrition intervention to promote healthy eating behaviors for birth to 36 months children with ASD, a developmentally critical period. In addition, if we found any positive trends/outcomes related to obesity as tested in our exploratory aim, this can inform the field of obesity and chronic disease prevention research, significantly relevant to public health.

## **16.0 Data Management and Confidentiality**

16.1

**Aim 1:** Descriptive statistics for quantitative data (i.e., mean, standard deviation, frequency and percentages) and content analyses for qualitative data (i.e., theme coding) will be performed based on information collected from the questionnaires.

**Aim 2:** Descriptive analyses of baseline characteristics and outcomes will include means and standard deviations for continuous variables and frequencies for categorical variables. Treatment compliance will also be evaluated. The primary analysis will be conducted based on the intent-to-treat principle. Distributional assumptions will be checked, and appropriate transformations or non-parametric methods will be applied as necessary.

**Aim 2a. Test the feasibility of enrollment, implementation, and evaluation of Autism Eats.** Descriptive statistics will be used to examine data distributions and frequencies. If there is substantial variability in attrition, completion, fidelity, and compatibility, we will examine the relations of such variables with any other variables we collect during the study such as demographic variables of EI providers and parent-child dyads.

**Aim 2b. To assess the preliminary efficacy of Autism Eats on child dietary intake and mealtime behaviors.** We will examine variance and effect sizes of key outcomes from pre- to post-intervention, as well as post-intervention to 5-month follow-up using non-

parametric tests and confidence intervals. We will first assess whether Autism Eats and EUC groups are balanced through randomization in terms of demographic variables at baseline. For each outcome variable, we will use boxplots and scatterplots with confidence intervals to visually inspect the changes across pre-intervention, post-intervention, and 5-month follow-up by group along with descriptive statistics. Also, nonparametric longitudinal analysis will be conducted for each outcome variable with time as a within-subject factor and treatment condition as a between-subject factor to examine the difference in changes between Autism Eats and EUC groups.

Exploratory Aim. We will explore whether weight status of children are different between Autism Eats and EUC groups at 5-month follow-up assessment. Descriptive statistics and visual inspection will be used to summarize weight status by group and effect sizes will be computed. Similar to the analysis of the primary outcomes, we will conduct nonparametric analysis to compare the changes in weight status at 5-month follow-up between Autism Eats and EUC groups. Note that parent BMI will be included as a covariate in the analysis.

16.2 Data will be collected and maintained in accordance with legal and ethical standards and will be centrally stored in a master database. RedCap is a secure web application for research studies in HIPAA compliant environments, which will be used to collect data, except the dietary intake data that will be collected through the ASA24 online system. RedCap will allow for data to be entered and uploaded to a central, secure database, while prohibiting access outside USF. Providers and parents will be emailed a link to the RedCap-based surveys.

Only principal investigator and study staff members will have access to files containing identifiers such as contact information of study participants (providers and parent-child dyads). These files will be stored in an encrypted form in a password protected secure database. These files will be used only for data collection.

The collected data will be deidentified. Participants' information that individuals can be identified with will be removed from the study data files. The deidentified data will be stored as study data files in a password protected USF computer in a locked USF office.

The Aim 2 study parent-child data will be submitted to the National Institute of Mental Health Data Archive (NDA) at the National Institutes of Health (NIH) as required for all NIH funded research studies collecting data from individuals with ASD. NDA is a large database where deidentified study data from many NIH studies are stored and managed. Sharing deidentified study data helps researchers learn new and important things about brain science more quickly than before. During and after the study, the study researchers will send deidentified study data about participants' health and behavior to the NDA. Other researchers across the world can then request the deidentified study data for different research projects. Every researcher (and the institution to which they belong) who requests the deidentified study data must promise to keep the data safe and promise not to try to learn participant identity. Experts at the NIH who know how to keep the data safe will review each request carefully to reduce risks to the participant privacy. Sharing the study data does have some risks, although these risks are rare. The study data could be accidentally shared with an unauthorized person who may attempt to learn participant's identity. The study researchers will make every attempt to protect the participant identity. NIMH will also report to Congress and on its website about the different studies using NDA data. The study participants will not be contacted directly about the study data submitted to NDA.

The study participants may decide that they do not want their study data to be added to NDA. They can still participate in this research study even if they decide that they do not want the data to be added to NDA. If any participants decide any time that they do not want the data to be added to NDA, we will let them call or email the study staff, and we will inform NDA to stop sharing the study data. Once the data is part of NDA, the study researchers cannot take back the study data that were shared before they were notified. The participants are informed about NDA on the consent form and the research staff will be explained through the informed consent process. Detailed NDA information is available on-line at <http://nda.nih.gov>.

16.3 Review of the rate of subject accrual and adherence to inclusion/exclusion criteria will occur monthly during the recruitment period. This will assure that participants will meet eligibility criteria and ethnic diversity goals outlined in the grant application.

Data type	Frequency of review
Subject accrual (adherence to protocol regarding demographics, inclusion/exclusion)	Monthly
Adverse events	As they happen
Adverse events rates	Bimonthly

Compliance to intervention	Bimonthly
Stopping rules regarding statistical power, implications of dropouts, and missing data	Semiannually

#### 16.4

All datasets will be de-identified with numeric numbers. The PI will have ultimate responsibility for ensuring participant well-being and for the integrity of data collection in the proposed study. The confidentiality of information provided by participants will be safeguarded by the use of participants' code numbers. In addition, all data will be stored in a locked file cabinet, and project staff will be instructed to maintain the participants' anonymity. All measurement protocols are well established in our research center and pose minimal risk. The data safety monitoring plan (DSMP) involves monitoring by the PI in conjunction with a safety officer from University of South Florida Institutional Review Board. There will be periodic reports by the project coordinator and [name] on data collected by the research team.

Only principal investigator and study staff members will have access to files containing identifiers such as contact information of study participants (providers and parent-child dyads). These files will be stored in an encrypted form in a password protected secure database. These files will be used only for data collection.

The collected data will be deidentified. Participants' information that individuals can be identified with will be removed from the study data files. The deidentified data will be stored as study data files in a password protected USF computer in a locked USF office.

For data security and confidentiality of study data files, we will develop data management and security policy that all users of the study data should adhere to. Only authorized users can have access to and possess the data files to conduct data analyses. Authorized users include principal investigator, study data managers, study data analysts. Other internal users and external users should be given authorization by the principal investigator. All users must sign a data security agreement and send a copy of the agreement to the principal investigator. Users should not share a copy of study data files. All users must adhere to the data security and confidentiality procedures. The study records and data will be maintained for 5 years after completion of the research, and will be destroyed based on the USF data disposal procedure and regulations.

#### 16.5

 Obtaining Signed Authorization	 Waiver of HIPAA Authorization for Recruitment/Screening Purposes Only
 Obtaining Online or Verbal Authorization (Alteration of HIPAA Authorization)	 Waiver of HIPAA Authorization for Entire Study
 Data Use Agreement	 Business Associate Agreement

- For Aim 1 of the study, we will not collect any PHI from participants. For Aim 2 of our study, children's clinical diagnosis of ASD or at risk/monitored for ASD is considered as a PHI because we will need to collect the ASD diagnosis or at risk/monitored for ASD status from the USF Epic. All USF Early Steps members have access to USF Epic and a liaison person to our research will verify the ASD diagnosis or at risk/monitored for ASD status under supervision of the director and co-investigator [name]. If the ASD diagnosis was performed outside the USF clinics or Early Steps program, the Early Steps usually have the information in file. We will ask the Early Steps to provide us with the ASD diagnosis or at risk/monitored for ASD status information for each child to confirm the eligibility before we obtain informed consent from the parents. We will not collect any PHI from the EI providers. Our parent consent/permission form for Aim 2 includes HIPAA language to indicate that such information is obtained for the purpose of the study.
- **Inclusion criteria:** The recruitment letters and flyers have the eligibility criteria about children's ASD diagnosis or at risk/monitored for ASD status. Children aged 0-36 months who are clinically diagnosed with ASD or at risk/monitored for ASD status within the Early Steps and their parents are eligible to participate in this study. After the EI providers shared the parent recruitment letter with the parents who are potentially eligible, parents who are interested in the study will contact the project coordinator or the principal investigator. Then, to determine children's eligibility before USF research staff obtain signed consent from parents, we will obtain a PHI (ASD diagnosis or at risk/monitored for ASD status) from the Early Steps program as described above. Therefore, we need to request a waiver of HIPAA authorization for recruitment/screening purposes only.
- **Time interval:** ASD diagnosis and at risk/monitored for ASD status verification process will be done twice: (1) one at the beginning of the enrollment process, prior to obtaining parent's informed consent; and (2) the other at the 5-month follow up assessment to capture any changes in ASD diagnosis or at risk/monitored for ASD status. The time interval between the ASD diagnosis verification and parent consent will be approximately 1-7 days. The second verification will be done around the time when the dyads complete the 5-month follow up assessment.
- **Plan to protect identifiers:** We will obtain the ASD diagnosis or at risk/monitored for ASD status PHI with de-identified numeric numbers. Study IDs and matched parent names will be separately provided to the Early Steps (see "ID and parent name tracking sheet.xlsx"). The Early Steps liaison staff will confirm the ASD diagnosis by looking up their USF Epic records and complete the ASD diagnosis tracking sheet using only the ID numbers without participants' names. The liaison staff will record ASD diagnosis or at risk/monitored for ASD status including who diagnosed ASD and determined at risk/monitored for ASD status, date of the evaluation, level of ASD (if reported), autism diagnostic observation schedule (ADOS) or alternative scale score (if reported), and child's age at diagnosis or evaluation date on "Early Steps ASD diagnosis tracking sheet.xlsx"). This ASD diagnosis tracking sheet does not include identifiable information. Only principal investigator and study staff members will have access

to the file containing identifiers (the ID and parent name tracking sheet), which will be stored separately from other data in a password protected secure database. They will be kept in a secure in Box that is HIPAA compliant.

- **Plan to destroy:** For individuals who agree to participate, their information will be kept as part of their research file and will be signing an authorization allowing for this information to be included in the research. Any PHI from those who are not eligible to participate or refuse to participate will be destroyed immediately.
- **Written assurance:** The PHI (ASD diagnosis or at risk/monitored for ASD status) will not be reused/disclosed to any other person or entity except as required by law, for authorized oversight of the research project, or for other research which use/disclose of PHI would be permitted by the HIPAA privacy regulations. Only de-identified data may be used for other research.
- **Why is not practicable to obtain signed HIPAA Authorization:** For Aim 2 of our study, the HIPAA waiver for screening and recruitment is needed to verify ASD diagnosis or at risk/monitored for ASD status prior to obtaining signed consent. After screening, signed authorization will be obtained through the parent consent/permission.
- **Why study cannot be conducted without access to PHI (ASD diagnosis or at risk/monitored for ASD status):** By collecting information from USF Epic regarding child's ASD diagnosis or at risk/monitored for ASD status, level of autism, and date of diagnosis/evaluation, we will obtain the most accurate information about clinical ASD assessment and diagnosis. The HIPAA waiver for screening and recruitment is needed to verify ASD diagnosis or at risk/monitored for ASD status prior to obtaining signed consent. There are cases with other developmental delays or disabilities such as down syndrome within the Early Steps programs. Because children with or at risk/monitored for ASD status experience specific mealtime and eating challenges and our intervention is designed to address those specific challenges, we need to know that children are diagnosed or at risk/monitored for ASD status prior to obtaining signed consent.
- **For Aim 2 of study, parent-child study data will be submitted to NDA as described in section 16.2. with Data Use Agreement completed by the PI and USF:** NIH-funded studies with human subjects who are diagnosed with ASD are required to submit deidentified data about health and behaviors of participants. Complying with this requirement, we have submitted the Data Use Agreement (DUA) and signed the Data Submission Agreement (DSA) on the NDA system. Any identifiable information will not be submitted to the NDA system.

## 17.0 Provisions to Monitor the Data to Ensure the Safety of Subjects

17.1 An adverse event (AE) is any untoward medical occurrence that is temporally associated with participation in the clinical study. A serious adverse event (SAE) is any adverse event that results in one or more of the following outcomes: death, life-threatening event, inpatient hospitalization or prolongation of existing hospitalization, persistent or significant disability/incapacity, congenital anomaly or birth defect, significant medical event based on clinical judgment.

AE severity will be graded by severity (mild, moderate, or severe) depending on the intensity of the event for the participant. An AE will be termed 'mild' if it does not have a major impact on the participant, 'moderate' if it causes the participant some minor inconvenience and 'severe' if it causes a substantial disruption to the participant's well-being. A participant can have a severe event that is not a SAE and a moderate event that meets the SAE definition. AE's will also be categorized according to the likelihood that they are related to the study intervention as: definitely, probably, possibly, or unrelated to the study intervention. SAEs that are unanticipated or possibly related to the study intervention will be reported to the Safety Officer at IRB and PI as they happen, and to the IRB, Clinical Research Center (CRC) and NIH within two weeks. Anticipated SAEs or those unrelated to the study intervention will be reported to the Safety Officer and PI as they happen, and to the IRB, CRC and NIH on a monthly basis.

There are multiple health professionals within the early intervention services. We will refer the subject to an appropriate professional counselor to address any adverse effect(s).

17.2 N/A

## **18.0 Provisions to Protect the Privacy Interests of Subjects**

18.1 All research activities will be conducted in private setting/platform with EI providers or research staff.

18.2 Subjects will provide informed consent.

## **19.0 Compensation for Research-Related Injury**

19.1 N/A

## **20.0 Subject Costs and Compensation**

20.1 There will be no cost incurred because of study participation that are over and above the costs that would be incurred from standard care or services.

20.2

 No Compensation	 Tokens (pens, food items, etc.)
 Financial Compensation (cash, gift cards)	 Other
 Course Credit (i.e. extra credit, SONA points)	

- Aim 1: Each EI provider and parent will receive \$50 for reviewing the intervention manual and materials.

- Aim 2: For both the Autism Eats intervention and We Can! EUC control groups,
  - Each EI provider will be compensated for the following activities,
    - First training session: a \$50 gift card
    - Second training session in the mid-point: a \$50 gift card
    - Completing intervention implementation: a \$50 gift card
    - Exit interview: a \$50 gift card.
    - Total amount: \$200
  - Each parent-child dyad will be compensated for the following activities,
    - Baseline assessment: a \$50 gift card
    - Post intervention assessment: a \$60 gift card
    - 5-month follow-up assessment: a \$70 gift card
    - Exit interview: a \$50 gift card
    - Total amount: \$230
- If any providers or parents participate in both Aim 1 and Aim 2 research activities, the maximum amount a provider can get from this study is \$250, and the maximum amount a parent-child dyad can get from this study is \$280. All participants (EI providers and parents), in both the intervention and EUC control group, will receive the same compensation schedule. There is no difference between the parent-child dyad intervention and control groups as it pertains to schedule.

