## 5.0 Procedures Involved

### 5.1

Aim 1: The EI providers (n=10) and parents (n=10) will be invited to review the intervention manual and materials and provide their feedback. Participants will receive a survey link for the manual review which is described in 5.2 below. Based on the results of the review, all intervention materials will be further refined and finalized.

Aim 2: The protocol for this project is designed to conduct a preliminary RCT. This pilot RCT compares Autism Eats (n=24 parent-child dyads) to the EUC condition using We Can! materials (n=24 parent-child dyads). EI providers (n=30) in two Florida counties (Hillsborough and Polk Counties) will be recruited on a rolling basis and parent-child dyads will be recruited through those EI providers. Baseline assessment will be scheduled. Study participants will be randomized into two intervention groups (Autism Eat and EUC We Can!) after collection of the baseline data. Random assignment will be conducted by [name] (Co-I) utilizing a random number generator. Participants in Autism Eats will receive the intervention components while those in the EUC group receive comparison We Can! materials. Data collection will be performed at three time points. Study design is also described in Figure 1.

5.2

 Audio/Video Recording	 Psychophysiological Recording
 Behavioral Interventions	 Record Review - Educational
 Behavioral Observations and Experimentations	 Record Review - Employee
 Deception	 Record Review- Medical
 Focus Groups	 Record Review - Other
 Interviews	 Specimen Collection or Analysis
 Investigational Device – Non-Significant Risk (e.g. Mobile Applications)	 Surveys and/or Questionnaires
 Psychometric Testing	 Other Social-Behavioral Procedures

**Aim 1:** We will invite EI providers and parents to review the intervention manual and materials and provide their feedback. The review invitation will be sent out through an online survey link (RedCap).

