For EI providers, the feasibility scale used in our pilot study will be used. Seven questions will address feasibility of implementing each lesson, clarity of instructions, relevance to the EI services, acceptability by parents, satisfaction of resources/references, and clarity and relevance to the overall goal. Open-ended questions on each lesson will allow EI providers to share recommendation regarding each session's content and materials. The manual review will take up to 3 hours per participant.

For parents, the feasibility scale will be tailored to parent participants and address clarity of instructions, acceptability, satisfaction of intervention materials, and feasibility of implementing feeding practices at home. Open-ended questions on each lesson will allow parents to share recommendation regarding each session's content and materials. The survey will take about 1-2 hours per participant.

**Aim 2:** We will track the number of EI providers and parents reached by the recruitment methods. We will monitor and document reasons for dropping out, and clearly indicate whether it was the provider or the parent who decide to drop out. Completion rates of assessments at all data collection time points, training sessions, and lesson and booster lesson implementation will be tracked and recorded.

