#### **Level 2 – Parent-child dyads:**

Inclusion criteria:

- Children should be enrolled in the EI service. Children who are determined as “at risk/monitored for ASD” at the time of screening or diagnosed with ASD determined by clinical assessment such as the Autism Diagnostic Observation Schedule (ADOS) or another validated evaluation tool such as Gilliam Autism Rating Scale (GARS-3). Children birth to 36 months are eligible for the EI

services, and therefore, age of our research participants will range from birth to 36 months.

- Parents should be 18 years or older and speak fluent English and/or Spanish

9.2

Level 1 – Early Intervention (EI) service providers:

Exclusion criteria: Non-EI service providers and who do not work with children with ASD.

Level 2 – Parent-child dyads:

Exclusion criteria:

- Children who are on exclusive breastfeeding, medicines that may interact with appetite and food consumption, having severe GI conditions such as irritable bowel syndrome, diagnosed with feeding disorders or severe food selectivity, or other serious medical comorbidities such as cancer.
- Parent and child with ASD who have previously participated in a similar nutrition intervention study will also be excluded.
- Parent's first language is not English or Spanish.

9.3 If participants are diagnosed with other serious illnesses or medication condition other than ASD, they will be excluded from the study. The intervention and EUC program will be implemented within the EI service schedules. EI providers and parent-child dyads work closely together within their regular EI programs regardless their participation status in our study. If either an EI provider or parent-dyad wish to withdraw from the study, it is likely that they will discuss and made a decision together.

9.4 The study will include employees from the USF Florida EI program, Early Steps, since the USF Early Steps EI providers will be recruited.

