## **22.0 Setting**

22.1 The study will be conducted at the USF College of Public Health (single site). The Florida EI service is called Early Steps. There are 15 Early Steps programs in Florida and the USF Early Steps program covers two counties (Hillsborough and Polk Counties). EI providers and parents from the USF Early Steps program in these two counties will be recruited for both Aim 1 and 2 of the study. For Aim 2, participants will be involved in weekly Autism Eats sessions or one EUC session through their regular EI services. The EI providers from the USF Early Steps program will be recruited on a rolling basis and parent-child dyads will be recruited through those EI providers. The director of the USF Early Steps program is a Co-investigator of the project ([name]) and there will be a project liaison staff person who will be paid to assist with the study recruitment and communication. [name] participated in protocol writing and has attended monthly project meetings since August 2021. All decisions regarding recruitment and participant engagement have been discussed with [name] and approved by her. Any further changes will be discussed with [name] at regular research team meetings.

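### People who reviewed the manual in Aim 1 may enter the Aim 2 trial, which can dilute the between-arm difference by an unstated amount and flatter some feasibility data

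*Protocol*

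**What the plan says.** In Aim 1, ten providers and ten parents "will be invited to review the intervention manual and materials and provide their feedback" (Protocol 5.1). The review goes through the whole program. For parents, "Open-ended questions on each lesson will allow parents to share recommendation" on its content, in a survey of about 1-2 hours; for providers, "The manual review will take up to 3 hours per participant" (Protocol 5.2). Parents also rate how feasible the feeding practices are at home.

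Providers and parents of the same two-county Early Steps program "will be recruited for both Aim 1 and 2 of the study" (Protocol 22.1). Aim 1 was planned to start in October 2021 and Aim 2 in January 2022 (Protocol 8.1). Section 20.2 caps total pay at $250 for a provider and $280 for a dyad "If any providers or parents participate in both Aim 1 and Aim 2 research activities".

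The nearest eligibility rule is in section 9.2 and applies to dyads only: "Parent and child with ASD who have previously participated in a similar nutrition intervention study will also be excluded". The provider exclusions cover job type and caseload. Aim 2 participants are randomised after baseline (Protocol 5.1; SAP, randomization section), and neither document describes stratification or restriction by Aim 1 status. The SAP's confounder list and missing-data text do not mention it either.

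**The concern.** By design, an EUC family receives one session based on a modified lesson 4, plus We Can! material (Protocol 5.3). A parent who has been through every lesson has seen content that this arm is meant not to receive. A provider who has studied every lesson may be the person who delivers EUC. The exposure would normally come before T1 and cannot be undone.

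The pilot's stated efficacy output is variance and effect sizes. If some participants gained part of the effect by reading, the estimated effect is too small, and a later trial planned from it would inherit the error.

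There is a second route. Aim 1 volunteers helped to shape the materials. If they also supply Aim 2 interviews, the feedback and compatibility findings come partly from people with a stake in them. They may also be readier than others to enrol, which would raise the reach figure.

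**Working it through.** **Inputs.**
- Aim 1: 10 parents and 10 providers (Protocol 5.1, 11.1).
- Aim 2: 48 dyads, 24 per arm, and 30 providers (Protocol 5.1, 11.1). The SAP's sample size section and Table 3 use 30 with 1:1 allocation, so 15 per arm. That mismatch is a separate matter; both sizes are carried here.
- Not in the documents, hence assumptions: k, the number of Aim 1 parents who enter Aim 2 (0 to 10); r, the share of the full effect obtained by reading (0 to 1); t, the part of that share already present at T1.

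**1. The plan's own figures.**
- Provider: 4 × 50 = 200 for Aim 2; 200 + 50 = 250.
- Dyad: 50 + 60 + 70 + 50 = 230; 230 + 50 = 280.

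Both caps equal the Aim 2 total plus the $50 Aim 1 payment, so dual participation is a foreseen case. The total of 146 individuals is 10 + 10 + 30 + 48 + 48, which counts nobody twice; with full overlap it would be 146 − 20 = 126 people.

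**2. Can reviewers land in EUC?** Assume that dyads are allocated 1:1. With only two overlapping parents among 48 dyads, the chance that at least one is in EUC is 1 − (24 × 23)/(48 × 47) = 1 − 552/2256 = 76%. With five it is about 98%, and with ten above 99.9%.

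**3. Effect on the difference in change.** Let E be the full effect, and suppose that an exposed Autism Eats dyad still ends at E.
- Exposed Autism Eats dyad: t × r × E is already in the baseline, so the change is E − t × r × E.
- Exposed EUC dyad: the part present at T1 cancels from the change. Only the later part counts, so the change is (1 − t) × r × E.
- Difference for exposed dyads: E × (1 − r), whatever t is.

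With p = k/N exposed in each arm on average, the contrast is E × (1 − p × r). The two routes divide r between them; they do not add to more than p × r.

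| k | p, N = 48 | p × r at r = 0.5 | p, N = 30 | p × r at r = 0.5 |
|---|---|---|---|---|
| 0 | 0 | 0 | 0 | 0 |
| 2 | 4.2% | 2.1% | 6.7% | 3.3% |
| 5 | 10.4% | 5.2% | 16.7% | 8.3% |
| 10 | 20.8% | 10.4% | 33.3% | 16.7% |

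At r = 1 the shrinkage equals p. These are averages over the randomisation. With k = 10, the number exposed in EUC has a 95% range of 2 to 8 (8-33% of 24, or 13-53% of 15), so a single trial can lie on either side.

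**4. Providers.** At most 10 of 30 (33%) could be Aim 1 reviewers. How many EUC dyads this reaches depends on whether providers or dyads are randomised. Protocol 5.1 speaks of participants being randomised, and section 4.1 of dyads assigned to EUC. No figure follows.

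**5. Reach.** Suppose that all ten Aim 1 parents agree when approached (an assumption). The 75% benchmark in SAP Table 3 is then reached when acceptance among other parents is (N − 10)/(N/0.75 − 10):
- N = 48: 38/54 = 70.4%.
- N = 30: 20/30 = 66.7%.

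**The case against.** The strongest reply is that nothing shows that any overlap will occur. Section 20.2 is a conditional pay cap, not an enrolment plan, and enrolment is rolling, so some Aim 1 children may pass 36 months before Aim 2 reaches them. This stands: the lower limit is zero.

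The exposure is also modest: one online review of a manual still to be refined, set against up to ten coached lessons and two boosters, while EUC receives a version of lesson 4 anyway. So r = 1 is a bound, not an expectation.

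A reader might infer that pre-baseline reading lowers the contrast through both arms at once. It does not. An effect fully present at T1 leaves the EUC change unaltered and reduces only the Autism Eats change; the EUC route needs an effect that emerges after T1. If an early gain faded in EUC, the contrast could even widen.

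A reader might also infer that reviewing providers would carry the material to about a third of EUC dyads (5 providers × 48/30 = 8 of 24). That needs provider-level randomisation, five reviewers in EUC and equal caseloads, none of which the documents state. Nor do they say where the earlier pilot's providers worked, so their entry into Aim 2 is conjecture.

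On feasibility, attrition and completion come from logs and records, and fidelity from observation. The worry is confined to feedback, part of compatibility and, through who agrees, reach.

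What the reply does not remove is the gap: dual participation is allowed, the dyad exclusion is unclear on it, the provider exclusions are silent, and the analysis cannot detect it as written.

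**Conclusion.** The point holds as a gap in eligibility and analysis, not as a demonstrated bias. If the prior-study exclusion covers Aim 1, sections 9.2 and 20.2 contradict each other for parents; if it does not, exposed parents may enter. For providers there is no rule at all.

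The likely direction is toward a smaller difference in change. That rests on two assumptions: full treatment brings exposed dyads to the same endpoint as others, and what is gained by reading lasts. For parents the size is between 0 and the k = 10 row of the table, with r = 0.5 as an illustration and r = 1 as the upper bound on average. The provider contribution is unknown. The favourable tilt in Aim 2a is inference. The certainty attaches to the permission and the missing safeguards, not to the amount.

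**What to change.** **Parents.** Add to section 9.2, Level 2: *Parents who reviewed the Autism Eats manual in Aim 1 are not eligible for Aim 2.* Align section 20.2 with this, keeping the payment cap for providers and for any parent already in both aims.

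**Providers, and parents already enrolled.** Record Aim 1 review, and any part in the earlier pilot, before randomisation (from the Aim 1 and pilot records for those already randomised). Report the numbers by arm. Give the Aim 2b estimates, and the Aim 2a reach and feedback, with and without these participants as a sensitivity analysis. Aim 1 review that precedes randomisation is a baseline characteristic, so leaving those dyads out keeps a randomised comparison.

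**Cost.** At most ten parents are lost from the recruitment pool, and one analysis is added. That analysis is less precise: if ten dyads are dropped and the standard error scales with 1/√N, it rises by √(48/38) − 1 = 12%, or √(30/20) − 1 = 22% with 30 dyads. Barring all ten Aim 1 providers is not proposed. Dyads are recruited through participating providers, and at 48/30 = 1.6 dyads each this could displace about 16 of 48. The planned Aim 2 start also precedes the latest logged protocol revision (September 2022), so the recording and sensitivity analysis may be the part that still applies.
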